On study tumor assessments	Tumor assessments that meet the following criteria: 1. No gap of ≥ 91 days between successive tumor assessments among those on or prior to the on study tumor assessment. (Note: a tumor assessment for which "Not Evaluated" is entered into the database does not qualify as a tumor assessment.) 2. No prior initiation of non-protocol anticancer therapy.
Overall response rate	The proportion of patients achieving a complete response or partial response to treatment.
Dose intensity	The total dose (in mg) a patient actually received divided by the total dose (in mg) the patient should have received had there been no missed doses, dosing delays or dosage reductions.
Intent-to-treat population	All patients randomized to receive study drug regardless of whether they actually received study drug and regardless of whether evidence is found indicating they failed to meet study inclusion/exclusion criteria or had other protocol violations.
Last contact date	The last contact date is the latest assessment/visit date recorded on any of the following case report forms: Discontinuation, Hematology, Chemistry, RECIST Overall Response Tumor Assessments, Survival Follow Up, Study Drug Infusion, Etoposide Infusion or Platinum Therapy Infusion.
Non-Protocol Anti-Cancer Therapy	Non-protocol anti-cancer therapies used by patients during their participation in this study, if any, will be identified by the sponsor after review of relevant data listings.
Per-protocol population	The subset of safety population who either (a) have at least one response evaluation on study, or (b) die prior to their first scheduled response evaluation.
Platinum Therapy / Platinum Choice	The physician's choice of platinum therapy (cisplatin or carboplatin) was used as a stratification variable by the dynamic randomization system. Discrepancies, if any, between the platinum therapy used to stratify a patient's treatment assignment and the platinum therapy actually administered during the study will be dealt with as follows. Platinum choice entered in the dynamic randomization system will be used in all efficacy analyses where platinum choice is included as a model

	effect. However, actual platinum received (as documented on earliest Platinum Therapy Infusion CRF [e.g., Cycle 1, Day 1]) will be used when calculating dosing compliance.

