2. STUDY OBJECTIVES

2.1. Primary Objectives

The primary objectives of this study are:

- Phase-1b portion: To determine the maximum tolerated dose (MTD) of tarextumab when administered on Day 1 of each 21 day cycle along with etoposide 100 mg/m² on Days 1, 2 and 3 and cisplatin 80 mg/m² or carboplatin to an area under curve (AUC) of 5 mg/mL/min on Day 1 in subjects with untreated extensive stage small cell lung cancer (ES-SCLC).
- Phase-2 portion: To determine the improvement in progression free survival (PFS) resulting from the addition of tarextumab to etoposide and platinum therapy (EP) in subjects receiving first-line therapy for ES- SCLC. (Platinum therapy for the phase-2 portion was similar to phase-1b [i.e., cisplatin or carboplatin], but the cisplatin dose was changed to 75 mg/m².)

Statistical analyses concerning the primary objective for the phase-1b portion of this study will not be addressed in this SAP.

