11.1.1. Dose Intensity

Dose intensity is defined as the total dose a patient actually received divided by the total dose the patient should have received had there been no missed doses, dosing delays or dosage reductions.

$$\text{Dose intensity} = \frac{\text{Total amount of drug received (mg)}}{\text{protocol-specified, planned amount of drug (mg)}}$$

The actual amount of drug received is obtained from the dosing records.

The protocol specified amount of drug to be received for each treatment is provided below.

Etoposide

The number of doses of Etoposide that should be administered per protocol is

$$3 \cdot \text{floor}\left(\frac{\text{Stop} - \text{Start}}{21}\right) + h_{\text{Etop}}\left[\frac{\text{Stop} - \text{Start}}{21} - \text{floor}\left(\frac{\text{Stop} - \text{Start}}{21}\right)\right],$$

where

$$h_{\text{Etop}}(x) = \begin{cases} 1 & \text{if } 21 \cdot x \geq 0 \\ 2 & \text{if } 21 \cdot x \geq 1 \\ 3 & \text{if } 21 \cdot x \geq 2 \end{cases}$$

Start is the date of the first dose of treatment. Stop is the last dose of treatment.

The amount of drug contained in a dose of Etoposide is

$$100\text{mg} / m^2 \cdot \text{BSA}$$

Carboplatin/Cisplatin/Study Drug

The number of doses of Carboplatin, Cisplatin or Study Drug that should be administered per protocol is

$$1 \cdot \text{floor}\left(\frac{\text{Stop} - \text{Start}}{21}\right) + h\left[\frac{\text{Stop} - \text{Start}}{21} - \text{floor}\left(\frac{\text{Stop} - \text{Start}}{21}\right)\right],$$

where

$$h(x) = \begin{cases} 1 & \text{if } 21 \cdot x \geq 0 \end{cases}$$

Start is the date of the first dose of treatment and Stop is the last dose of treatment for the respective drugs. Treatment period is (last treatment date – first treatment date + 2), allowing 2 extra days to cover any following early visits.

The mg amount of drug contained in a dose of Carboplatin is

$$(\text{AUC of 5}) \times (\text{GFR} + 25)$$

The mg amount of drug contained in a dose of Cisplatin is

$$80\text{mg} / \text{m}^2 \times \text{BSA}$$

The amount of drug contained in a dose of study drug is

$$15\text{mg} / \text{kg} \cdot \text{weight}$$

Weight, BSA and GFR are to be determined at each visit. Use the latest weight, BSA and/or GFR on or before each dose to determine the amount of drug (mg) in a dose.

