Min, Max	xx, xx	xx, xx
Number of Infusions Administered		
n	xx	xx
Mean (SD)	xx.x (xx.xx)	xx.x (xx.xx)
Median	xx	xx
25 th , 75 th Percentile	xx, xx	xx, xx
Min, Max	xx, xx	xx, xx
Total Dose Administered (mg) ^[1]		
n	xx	xx
Mean (SD)	xx.x (xx.xx)	xx.x (xx.xx)
Median	xx	xx
25 th , 75 th Percentile	xx, xx	xx, xx
Min, Max	xx, xx	xx, xx
Duration of Treatment (days) ^[2]		
n	xx	xx
Mean (SD)	xx.x (xx.xx)	xx.x (xx.xx)
Median	xx	xx
25 th , 75 th Percentile	xx, xx	xx, xx
Min, Max	xx, xx	xx, xx
Dose Intensity		
n	xx	xx
Mean (SD)	xx.x (xx.xx)	xx.x (xx.xx)
Median	xx	xx
25 th , 75 th Percentile	xx, xx	xx, xx
Min, Max	xx, xx	xx, xx

^[1] Placebo exposure is summarized in tarextumab-equivalent units (i.e., the number of milligrams of tarextumab the placebo “replaced” during treatment-blinded dosing).

^[2] Duration of treatment = number of days from the first dose (Day 1) until the last dose.

Table 14.3.5.2
Dosing Compliance – Tarextumab/Placebo
Safety Population

	Placebo (N=xx)	Tarextumab (N=xx)
Dosing Compliance (%) ^[1]		
n	xx	xx
Mean (SD)	xx.x (xx.xx)	xx.x (xx.xx)
Median	xx	xx
25th, 75th Percentile	xx, xx	xx, xx
Min, Max	xx, xx	xx, xx
0% to <20% Dosing Compliance	xx (xx.x%)	xx (xx.x%)
20% to <40% Dosing Compliance	xx (xx.x%)	xx (xx.x%)
40% to <60% Dosing Compliance	xx (xx.x%)	xx (xx.x%)
60% to <80% Dosing Compliance	xx (xx.x%)	xx (xx.x%)
80% to <100% Dosing Compliance	xx (xx.x%)	xx (xx.x%)
100% Dosing Compliance	xx (xx.x%)	xx (xx.x%)
Number of Missed Doses	xx	xx
Reason for Missed Dose		
Adverse Event	xx	xx
Other	xx	xx
Number of Delayed Doses	xx	xx
Reason for Delayed Dose		
Adverse Event	xx	xx
Other	xx	xx
Number of Reduced Doses	xx	xx
Reason for Reduced Dose		
Adverse Event	xx	xx
Other	xx	xx

^[1] Dosing compliance = (number of doses administered) / number of planned doses x 100.

Table 14.3.5.3
Study Drug Exposure – Etoposide
Safety Population

	Placebo (N=xx)	Tarextumab (N=xx)
Treatment Cycles		
n	xx	xx
Mean (SD)	xx.x (xx.xx)	xx.x (xx.xx)
Median	xx	xx
25 th , 75 th Percentile	xx, xx	xx, xx
Min, Max	xx, xx	xx, xx
Number of Infusions Administered		
n	xx	xx
Mean (SD)	xx.x (xx.xx)	xx.x (xx.xx)
Median	xx	xx
25 th , 75 th Percentile	xx, xx	xx, xx
Min, Max	xx, xx	xx, xx
Total Dose Administered (mg)		
n	xx	xx
Mean (SD)	xx.x (xx.xx)	xx.x (xx.xx)
Median	xx	xx
25 th , 75 th Percentile	xx, xx	xx, xx
Min, Max	xx, xx	xx, xx
Duration of Treatment (days) ^[1]		
n	xx	xx
Mean (SD)	xx.x (xx.xx)	xx.x (xx.xx)
Median	xx	xx
25 th , 75 th Percentile	xx, xx	xx, xx
Min, Max	xx, xx	xx, xx

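### SAP 11.1.1: the two-day early-visit allowance enters neither planned-dose formula, so a slightly early last cycle pushes dose intensity above 100%

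*SAP*

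**What the plan says.** The Definitions list of the SAP defines dose intensity as the total dose received "divided by the total dose (in mg) the patient should have received had there been no missed doses, dosing delays or dosage reductions". Section 11.1.1 repeats the definition and gives two formulas for the planned number of doses.

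- **Etoposide:** 3 × floor((Stop − Start)/21), plus 1, 2 or 3 according to the remainder in days. "Start is the date of the first dose of treatment. Stop is the last dose of treatment".
- **Carboplatin, cisplatin and study drug:** floor((Stop − Start)/21) + 1. "Start is the date of the first dose of treatment and Stop is the last dose of treatment for the respective drugs".

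After the second definition comes a further sentence: "Treatment period is (last treatment date – first treatment date + 2), allowing 2 extra days to cover any following early visits". The term it defines appears in neither formula. It is not the interval of the exposure tables either. The footnote to the Table 14.3.5.1 shell in Appendix B reads "Duration of treatment = number of days from the first dose (Day 1) until the last dose", with no added days.

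**The concern.** The section gives two intervals for the same count and does not say which one applies, or to which drugs. The early-visit sentence shows that the problem was foreseen, but the correction is attached to nothing. Two programmers working from this text, including the independent validator required by section 5.1, could produce different denominators for the same patient.

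Under the SAP's own definition, a patient who receives every dose in full and is never late should score 1. As printed, that patient scores above 1 whenever the last cycle is a day or two early. The same undercount can cancel a dose that was really missed. The rows at stake are the dose-intensity summaries in Tables 14.3.5.1, 14.3.5.3, 14.3.5.5 and 14.3.5.7.

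**Working it through.** **Inputs.** From section 3.1: 21-day cycles, platinum and study drug on Day 1, etoposide on Days 1, 2 and 3, and six cycles of chemotherapy. From section 11.1.1: the two formulas. Write d = Stop − Start in days. For etoposide the conditions on the remainder overlap, so the highest one met is taken. Early means early against the 21-day grid counted from the first dose.

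**On schedule, six cycles.**
- Platinum or study drug: d = 5 × 21 = 105, so floor(105/21) + 1 = 6 planned.
- Etoposide: Stop is Day 3 of cycle 6, so d = 105 + 2 = 107 and 3 × 5 + 3 = 18 planned.

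Both counts are right, so the formulas work when the last cycle is on the grid.

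**Study drug or carboplatin, all doses given in full, last dose one or two days early.**

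| Doses given | d (1 / 2 days early) | Planned as printed | Ratio |
|---|---|---|---|
| 2 | 20 / 19 | 1 | 200% |
| 3 | 41 / 40 | 2 | 150% |
| 4 | 62 / 61 | 3 | 133% |
| 6 | 104 / 103 | 5 | 120% |
| 8 | 146 / 145 | 7 | 114% |
| 10 | 188 / 187 | 9 | 111% |
| 12 | 230 / 229 | 11 | 109% |

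With d + 2 in the formula, every row returns the number of doses given and a ratio of 100%.

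**Etoposide, all doses given in full.**

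| Cycles (doses) | 1 day early | 2 days early |
|---|---|---|
| 2 (6) | d = 22, 5 planned, 120% | d = 21, 4 planned, 150% |
| 4 (12) | d = 64, 11 planned, 109% | d = 63, 10 planned, 120% |
| 6 (18) | d = 106, 17 planned, 106% | d = 105, 16 planned, 112.5% |

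**Hidden missed dose.** Five of six scheduled study-drug or carboplatin doses are given and d = 104. As printed, 5/5 = 100%. With the two days, floor(106/21) + 1 = 6 and the ratio is 5/6 = 83%.

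**Why two days cannot simply be added to the etoposide formula.** A patient who stops on time after Day 1 of cycle 6 has d = 105 and 3 × 5 + 1 = 16 planned, which is correct. With d + 2 = 107 the count becomes 3 × 5 + 3 = 18, and 16 doses score 16/18 = 89%. The allowance has to act on the cycle count and leave the Day 1, 2 or 3 term alone.

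**Cisplatin.** Its milligram ratio carries a second, separate error. Section 11.1.1 prices a planned cisplatin dose at 80 mg/m², whereas section 2.1 says of phase 2 "but the cisplatin dose was changed to 75" mg/m². The factor is 75/80 = 0.9375. As printed, an early last cycle therefore gives 6/5 × 0.9375 = 112.5% at six doses, 4/3 × 0.9375 = 125% at four and 2 × 0.9375 = 187.5% at two. Mending the interval alone gives 93.75%, not 100%.

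**The case against.** The best reply is that this is loose drafting. The early-visit sentence stands directly under the platinum and study-drug formula and states its purpose, so a sensible programmer would put the two days in, and the 120% to 200% figures would not arise. That reading is plausible, but Start and Stop are explicitly defined as dose dates, so following the formula literally leaves the two days out. The sentence also does not settle etoposide, where adding two days to the printed formula gives a different wrong answer.

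Several other points stand and limit the finding.

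- Etoposide is less exposed. Because Stop is normally Day 3, the whole-cycle count survives a last cycle one or two days early, and only the Day 1, 2 or 3 term slips.
- How often it happens is unknown. A net delay in an earlier cycle offsets an early last cycle, and the SAP gives no dosing window. The 150% and 200% figures for study drug or carboplatin need a patient who stopped after three or two doses.
- The ratios for 8 to 12 study-drug doses do not apply after prophylactic cranial irradiation. Section 3.1 requires at least 14 days without study drug before it and 14 after, so the gap is at least 28 days against a 21-day cycle. Such a patient is at least 7 days behind the grid.
- The cisplatin figures mix in the separate 80 versus 75 mg/m² error.
- Missed and delayed doses and dosing compliance are tabulated separately, so a missed dose hidden in dose intensity is still visible elsewhere.

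**Conclusion.** The concern holds: the section is wrong as written. The printed planned-dose rule contradicts the SAP's definition of dose intensity for any fully dosed, undelayed patient whose last cycle is one or two days early, and the sentence meant to prevent this is connected to no formula. At six cycles the overstatement is 20 percentage points for study drug or carboplatin, and 6 or 12.5 points for etoposide. It is larger for short courses and smaller for long ones.

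These sizes assume full doses and a last cycle early against the grid from the first dose. The share of patients meeting that condition is unknown. So is the net effect on the mean, because delays and irradiation holds pull the ratio down. The reach is confined to descriptive exposure rows. The correction should be made because it is cheap and the text cannot be programmed unambiguously.

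**What to change.** - **Platinum and study drug:** replace Stop − Start by Stop − Start + 2 in both the floor and the remainder term, and delete the free-standing treatment-period sentence.
- **Etoposide:** planned doses = 3 × floor((Day 1 of last cycle − Day 1 of first cycle + 2)/21), plus 1, 2 or 3 for the day of the last dose within the last cycle. Six full cycles that end zero, one or two days early give 3 × 5 + 3 = 18. An on-time stop on Day 1 of cycle 6 stays at 3 × 5 + 1 = 16.
- **State the limits.** A last cycle three days early is still undercounted: 6/5 = 120% for study drug or carboplatin (d = 102) and 18/15 = 120% for etoposide. A last platinum or study-drug dose 19 or 20 days late now adds a planned dose (d = 124 gives floor(126/21) + 1 = 7, so 6/7 = 86%), whereas the printed rule does so only at 21 days. For etoposide at the same delay the count becomes 3 × 6 + 3 = 21, against 19 or 20 as printed.

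The cost is a one-line change to each of the two formulas in the SAP and the program. No new data are needed: the etoposide infusion listing (16.2.5.2) already carries the visit and infusion date. The cisplatin dose of 80 mg/m² in the same section needs its own correction to 75.

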11.1.2. Dosing Compliance

Dosing compliance is defined as the ratio of the number of doses administered to the number of doses planned according to the schedule outlined in the study protocol.

$$\text{Dosing compliance} = \frac{N_{\text{administered}}}{N_{\text{planned}}} \times 100\%$$

where N_{planned} is the number of doses planned according to the schedule outlined in the study protocol and $N_{\text{administered}}$ is the number of doses the patient received.

Dosing compliance will be summarized as a continuous variable (see Section 5) and by the numbers of patients with 0% to <20%; 20% to <40%; 40% to <60%; 60% to <80%; 80% to <100%; and 100% compliance. The reasons for delaying and/or withholding doses randomized study drug, selected platinum agent and etoposide will also be summarized.

11.2. Adverse Events

Reported AE terms will be mapped to preferred terminology using Medical Dictionary for Regulatory Activities (MedDRA) version 17.1. All reported events will appear in AE listings, however only treatment-emergent adverse events will be summarized. A treatment-emergent adverse event (TEAE) is an AE that starts or increases in severity any time after the first administration of any randomized study drug (i.e., tarextumab or placebo) up to 30 days following the last administration of any study drug. AE severity was rated by the investigator according to Common Terminology Criteria for Adverse Events (CTCAE) version 4.03 criteria.

A high-level safety summary will display the numbers of patients within each treatment arm who experience one or more AEs in each of the following categories:

- All TEAEs regardless of severity or presumed relationship to study drug
- TEAEs judged related to tarextumab/placebo
- TEAEs judged related to etoposide
- TEAEs judged related to platinum therapy (cisplatin or carboplatin)
- TEAEs judged related to any study drug
- Treatment-emergent SAEs regardless of severity or presumed relationship to study drug
- Treatment-emergent SAEs judged related to tarextumab
- Treatment-emergent SAEs judged related to EP
- Treatment-emergent SAEs judged related to any study drug
- TEAEs leading to a delay/interruption in the administration of study drug
- TEAEs leading to a reduction in the protocol-specified dose of study drug
- TEAEs leading to discontinuation of study drug
- TEAEs leading to withdrawal from the study
- TEAEs leading to death

The base summary of TEAEs will show treatment-arm incidence rates for each MedDRA primary system organ class (SOC) and/or preferred term (PT) sorted by descending incidence in the tarextumab treatment group. A separate summary will be produced for each of the AE subsets listed above. Additional summaries will be produced by CTCAE severity grade. Patients may have more than one TEAE per MedDRA SOC and/or PT. At each level of summarization, a patient is counted once if he or she reported one or more TEAEs at that level. In AE summaries by CTCAE severity grade, patients will be classified according to the highest reported CTCAE severity for a qualifying event.

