2.2. Secondary Objectives

The secondary objectives of this study are:

- Phase-1b and -2 portions: To determine the PK of tarextumab in combination with EP in subjects receiving first-line therapy for ES-SCLC
- Phase-1b and -2 portions: To determine the immunogenicity of tarextumab in combination with EP in subjects receiving first-line therapy for ES-SCLC
- Phase-2 portion: To estimate the improvement in overall survival (OS), 12-month survival and overall response rate (ORR) resulting from the addition of tarextumab to EP in subjects receiving first-line therapy for ES-SCLC

- Phase-2 portion: To correlate the treatment effect in PFS, OS, 12-month survival and ORR resulting from the addition of tarextumab to EP in subjects with Notch3, Hey2, Hes1, Hey1 and Hes6 expression
- Phase-1b portion: To determine the safety and tolerability of tarextumab in combination with EP in subjects who are receiving first-line therapy for ES-SCLC
- Phase-2 portion: To compare the safety and tolerability of tarextumab in combination with EP relative to EP alone in all subjects who are receiving first-line therapy for ES-SCLC

Statistical analyses concerning the secondary objectives for the phase-1b portion of this study will not be addressed in this SAP.

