investigator should receive PCI within 8 weeks after the last dose of chemotherapy at a total dose of 25 Gy in 10 fractions. If subjects discontinue EP with treatment-related toxicities prior to completing 6 cycles and are good candidates for PCI per the investigator, PCI can be initiated at any time determined appropriate by the investigator. Subjects who do not receive PCI within 8 weeks after the last dose of chemotherapy can have PCI later during the study as determined by the investigator. Study drug (tarextumab or placebo) administration should continue at every 21-day cycle between the completion of chemotherapy and the initiation of PCI. PCI should not be initiated within 2 weeks of study drug administration and study drug will be held during the PCI treatment period. Subjects will resume study drug alone ≥ 14 days after completion of PCI, until disease progression or unacceptable treatment-related toxicities or withdrawal of consent. Subjects will discontinue study treatment if there is evidence of central nervous system (CNS) metastasis.

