Subjects Reporting TEAE Leading to Delay/Interruption of Platinum Therapy	xx (xx.x%)	xx (xx.x%)
Subjects Reporting TEAE Leading to Dose Reduction of Study Drug ^[1]	xx (xx.x%)	xx (xx.x%)
Subjects Reporting TEAE Leading to Dose Reduction of Etoposide	xx (xx.x%)	xx (xx.x%)
Subjects Reporting TEAE Leading to Dose Reduction of Platinum Therapy	xx (xx.x%)	xx (xx.x%)
Subjects Reporting TEAE Leading to Withdrawal of Study Drug ^[1]	xx (xx.x%)	xx (xx.x%)
Subjects Reporting TEAE Leading to Withdrawal of Etoposide	xx (xx.x%)	xx (xx.x%)
Subjects Reporting TEAE Leading to Withdrawal of Platinum Therapy	xx (xx.x%)	xx (xx.x%)
Subjects Reporting TEAE with Outcome of Death	xx (xx.x%)	xx (xx.x%)
Maximum CTCAE Severity Grade ^[2]		
Grade 1	xx (xx.x%)	xx (xx.x%)
Grade 2	xx (xx.x%)	xx (xx.x%)
Grade 3	xx (xx.x%)	xx (xx.x%)
Grade 4	xx (xx.x%)	xx (xx.x%)
Grade 5	xx (xx.x%)	xx (xx.x%)

^[1] Study drug = tarextumab or placebo.

^[2] CTCAE = Common Terminology Criteria for Adverse Events (version 4.02). Subjects with more than one TEAE are counted only once at the highest CTCAE severity grade across all TEAEs.

Table 14.3.1.2
Treatment-Emergent Adverse Events (TEAEs) by System Organ Class and Preferred Term
Safety Population

System Organ Class / Preferred Term	Placebo (N=xx)	Tarextumab (N=xx)
Subjects Reporting at Least One Qualifying TEAE	xx (xx.x%)	xx (xx.x%)
System Organ Class 1		
Preferred Term 1.1	xx (xx.x%)	xx (xx.x%)
Preferred Term 1.2	xx (xx.x%)	xx (xx.x%)
Preferred Term 1.3	xx (xx.x%)	xx (xx.x%)
[etcetera]	[:]	[:]
System Organ Class 2		
Preferred Term 2.1	xx (xx.x%)	xx (xx.x%)
Preferred Term 2.2	xx (xx.x%)	xx (xx.x%)
Preferred Term 2.3	xx (xx.x%)	xx (xx.x%)
[etcetera]	[:]	[:]

Note: At each level of summation (overall, system organ class, preferred term), subjects reporting more than one adverse event are counted only once.

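### Adverse events are compared only as crude patient percentages over a window that follows time on drug, so the arms can differ at equal monthly risk if time on drug differs

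*SAP*

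**What the plan says.** A phase-2 secondary objective in SAP section 2.2 is "To compare the safety and tolerability of tarextumab in combination with EP relative to EP alone in all subjects".

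Section 11.2 summarizes only treatment-emergent adverse events (TEAEs). The window opens at the first dose of randomized drug and runs "up to 30 days following the last administration of any study drug". Section 3.1 continues randomized drug after chemotherapy "until disease progression or unacceptable treatment-related toxicities or withdrawal of consent".

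Section 11.2 describes the main table as follows: "The base summary of TEAEs will show treatment-arm incidence rates for each MedDRA primary system organ class (SOC) and/or preferred term (PT"). These rates have no time denominator. The section goes on to say that "a patient is counted once if he or she reported one or more TEAEs at that level", and the shell for Table 14.3.1.2 repeats that "subjects reporting more than one adverse event are counted only once". The TEAE shells show n (%) under the arm total.

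Person-years appear only in the survival-type shells (OS, PFS, duration of response, and the antibody-status versions of PFS and OS). Cycles, infusions and days on treatment are tabulated by arm in Tables 14.3.5.x but do not enter any adverse event table. Section 8.1 plans a PFS analysis for the combination chemotherapy period (Table 14.2.2.3). There is no adverse event counterpart.

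**The concern.** How long a patient is watched for TEAEs depends mainly on how long the patient stays on drug, and that depends largely on the primary endpoint. Section 6 sizes the trial for a shift in median PFS from 4.8 to 7.2 months. If that shift occurs, the plan itself implies unequal windows. A percentage of patients with at least one event rises with the length of the window, so two arms with the same monthly risk would show different percentages.

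The safety comparison is at stake. A modest excess on tarextumab could be toxicity or only longer observation. If tarextumab were given for less time, a real excess could be hidden. The planned tables cannot separate these. The exposure tables show that time on drug differs, but they do not let a reader adjust the percentage for a given event.

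**Working it through.** **1. The design effect.** The SAP gives no adverse event figure, so the anchor is its power statement: 91 PFS events, HR 0.67, one-sided alpha 0.15 (Table 1).

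Power = Φ(√91/2 × |ln 0.67| − 1.036) = Φ(4.770 × 0.4005 − 1.036) = Φ(0.874) = 0.809. Table 1 gives 0.8090. The medians agree with this HR: 4.8/7.2 = 0.667.

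**2. Inputs for the window.**
- Control PFS hazards from Table 3: 0.1386 (0–5 months), 0.3466 (5–7), 0.6931 (7–8), then 0.1386, the late value used for Table 2. It is applied here from month 8, where the last Table 3 interval starts. The two late values in Table 3, 0.0693 and 0.2310, serve as the range.
- HR 0.65 for tarextumab (Table 3).
- Entry times interpolated from the Table 2 enrolment row, up to 134 patients.
- Cuts at month 22, where Table 2 expects 90 PFS events (close to the planned 91), and at month 26.
- Window = min(PFS time + 30 days, time from entry to cut), with 30 days = 30/30.44 = 0.986 month.

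Two inputs are assumptions, not SAP figures: every patient takes drug until progression, and the first-event rate L is constant and equal in both arms.

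**3. Formula.** P(at least one TEAE) = 1 − E[exp(−L × window)]. L is set so that placebo shows 10, 20, 30 or 50%, and the same L is then applied to the tarextumab window (400,000 simulated patients per arm).

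| Cut | Mean window, placebo vs tarextumab (months) | 10% becomes | 20% becomes | 30% becomes | 50% becomes |
|---|---|---|---|---|---|
| Month 22 | 5.4 vs 6.4 (ratio 1.20) | 11.8 | 23.3 | 34.5 | 55.6 |
| Month 26 | 5.9 vs 7.4 (ratio about 1.25) | 12.3 | 24.2 | 35.7 | 57.1 |

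The excess is about 2 to 6 points at month 22 and 2 to 7 at month 26. Late hazards of 0.0693 or 0.2310 move the percentages by less than 0.5 point.

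**4. Cross-check without a data cut.** With exponential PFS and μ = ln 2/median, P = 1 − exp(−0.986 L) × μ/(μ + L). At L = 0.05 per month:
- placebo (median 4.8): 1 − 0.952 × 0.1444/0.1944 = 29.3%;
- tarextumab (median 7.2): 1 − 0.952 × 0.0963/0.1463 = 37.3%.

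For L from 0.01 to 0.2 the excess is 3 to 9 points.

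**5. Where the effect shrinks or turns.**
- Events confined to the six 21-day cycles plus 30 days, month-26 cut: 10/20/30/50% becomes 10.7/21.4/32.0/52.9%, an excess of 0.7 to 2.9 points. The mean window is then 4.14 vs 4.44 months, ratio 1.07.
- Stopping before progression at an assumed 0.05 or 0.10 per month in both arms: 20% becomes 23.3% or 22.7% instead of 24.2%.
- Equal time on drug: no excess.
- Tarextumab stopped earlier (assumed median time on drug 3.6 vs 4.8 months, exponential, L = 0.05): 24.4% on tarextumab vs 29.3% on placebo at equal risk.

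**6. Does one exposure-adjusted rate solve it?** If L is constant throughout, first events per patient-month at risk give a ratio of 1.00. If events occur only in the EP period, at the same rate in both arms, a rate over the whole window gives a tarextumab/placebo ratio of about 0.85 to 0.91 at month 26. The low-risk maintenance time enlarges the tarextumab denominator. Restricting both events and time to the EP period brings the ratio back to about 1.00.

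**The case against.** The strongest reply is that this is the conventional TEAE summary. It is clearly defined, the shells match it, and it is the same in both blinded arms. All of that is true. A reader might infer that the rule itself is tilted against tarextumab. The SAP does not support that: the windows differ only if progression or tolerability differs, and the direction can go either way.

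The modelled excess is also near the upper end within its own model. Section 3.1 allows stopping for toxicity or withdrawal and holds drug during cranial irradiation, and early chemotherapy toxicity is little affected. With about 67 patients per arm (134/2), the standard error of a difference, √(2p(1−p)/67), is 5.2, 6.9, 7.9 and 8.6 points at 10, 20, 30 and 50%. Each modelled excess is below one standard error. The tables carry no tests, so no formal inference is distorted. This limits the size of the problem, but the distortion is systematic: it pushes every event type that accrues on maintenance in the same direction.

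The reversal is weaker than it first looks. The window closes after the last dose of any study drug, and section 7.1 counts platinum and etoposide among the study drugs. On that reading, a patient who stops tarextumab early stays in the window while EP continues. The reversal then matters mainly after EP ends.

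Finally, treatment duration is tabulated by arm and the adverse event listing gives onset days. A reader can therefore see unequal exposure, but no planned summary adjusts for it.

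**Conclusion.** The point holds in conditional form. The plan compares TEAEs between arms only by crude percentages over a window tied to time on drug. If time on drug differs, those percentages differ at equal monthly risk. Under the SAP's own hazards and accrual the spurious excess is about 2 to 7 points at month 26 and 2 to 6 at month 22, for a constant event rate and drug given until progression. It is about 1 to 3 points for events confined to the EP period, zero with equal time on drug, and can reverse. The event rates and the treat-to-progression assumption are not in the SAP.

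Two stronger readings are not supported. The documents do not show that tarextumab must display more adverse events, because that requires longer time on drug. Nor does the point justify resting the safety conclusion on a whole-window exposure-adjusted rate, which would look falsely reassuring (ratio about 0.85 to 0.91) if events cluster in the EP period. The primary analysis is untouched. The change is worth making because it is cheap and serves a stated secondary comparison.

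**What to change.** In section 11.2:

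- Keep the n (%) tables and call their entries crude percentages rather than incidence rates.
- For all TEAEs, grade 3 or higher, serious and fatal TEAEs and the common preferred terms, add exposure-adjusted first-event incidence by arm: patients with a first event divided by patient-months at risk.
- Show it separately for two periods. The EP combination period runs from first dose to 30 days after the last EP dose, ending earlier at the end of the TEAE window or at the data cutoff. The single-agent period is the remainder of the TEAE window.
- State whether a first event means first in the period or first on study.
- Read the between-arm comparison from the crude and period-specific summaries together, not from one whole-window rate.

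The cost is SAP wording and a few extra tables from infusion and onset dates already listed. The rates assume a roughly constant hazard within each period. The single-agent comparison covers only patients who reach that period, so it is descriptive.
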